### Risk analysis

Beta-lactam antibiotics are generally very well tolerated. The most serious potential risk is anaphylaxis which is reported in 1-5/10,000 doses. As per usual clinical practise, patients will have their allergy status checked pre-operatively and those with a known relevant allergy excluded from the trial. For those included, we have no reason to believe that continuous infusion is any more likely to result in an allergic reaction than bolus dose. The risk above standard treatment with in this study protocol is the higher dose of cefuroxime required to achieve the target a serum level of 64mg/L for the duration of surgery (53% <3 hours, 95% < 6 hours). Cefuroxime levels above 64mg/L are surpassed after bolus administration of intravenous therapy. But due to cefuroxime's short half life (1.5 hours) these levels normally fall over the following hours. Continuous infusions of beta-lactam antibiotics, in order to achieve continuously targeted serum concentrations of up to 100mg/L, have been administered for days of treatment without reported adverse events (Moriyama 2010). Other beta-lactams e.g. piperacillin, are given at 4g in a single dose (repeated 8 hourly). Cefuroxime can be dosed at higher doses (higher dose 3g 8 hourly, vs standard dose 1.5 g 8 hourly) for meningitis. This suggests targeting cefuroxime serum levels of 64mg/L for up to 6 hours is unlikely to result in dose related adverse events. See section 8.6 for full details of the study intervention dosing regimen.

An assessment of adverse events associated with cefuroxime is provided in the products SPC:  
<https://www.medicines.org.uk/emc/medicine/16929>

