#### 3.6 Exploratory endpoints/outcomes

Table 5: Exploratory endpoints		
Objectives	Outcome Measures	Timepoint(s) of evaluation of this outcome measure (if applicable)
To explore the impact of the antibiotic susceptibility of rectally colonising Enterobacteriaceae on the	Minimum Inhibitory Concentration of the Predominant Enterobacteriaceae	Pre-operative

efficacy of antibiotic prophylaxis in patients receiving standard antibiotic dosing, and in patients receiving PD target based dosing.
	
Minimum Inhibitory Concentration of the most resistant Enterobacteriaceae
 
Minimum Inhibitory Concentration of the predominant E. coli.
 
Surgical site infection rate within 30 days of operation
	

To determine exposure response relationships within patients treated with standard antibiotic dosing.
	
Free serum drug levels
 
MICs of colonising Enterobacteriaceae
 
Exposure response relationships including:
 
fT>MIC
 
CMAX/MIC
	
1,2,3 and 4 hours post initiation of antibiotic prophylaxis.

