### 7.11 Storage and analysis of samples

Criteria for the collection, analysis, storage and destruction of biological samples

Rectal swab

- Testing location: Old Medical School, Leeds General Infirmary.
- Timings of testing: Pre-operative
- Shipping details: Clinical transport system
- Sample destruction: At the end of the laboratory studies have been completed, not expected to be > 1 year after date of the participant recruitment.
- Sample storage
  - o Conditions: 4 degrees Celsius +/- 5 degrees Celsius
  - o Duration: As sample destruction
  - o Location: as testing location
  - o Long term storage: None
- Laboratory manual: Available in the Old Medical School, Leeds General Infirmary

Blood samples for antibiotic drug concentrations

- Whole blood
- 6 ml
- Blood tube: Serum separator tube
- Testing location: Southmeads antimicrobial reference laboratory.

- Timings of testing: 4 samples taken intra-operatively. One sample will be collected at approximately 10 minutes after antibiotic infusion. One sample will be collected prior to closing the surgical wound. The other two samples will be taken after the surgery is approximately 1/3rd and 2/3rds complete. If a patient is re-dosed intra-operatively one of these two samples can be moved to be taken prior to the re-dosing.
- Shipping details: On ICE to Southmeads Antibiotic reference laboratory
- Sample destruction: As per Southmeads local guidelines (not more than 7 days of result)
- Sample storage
  - o Conditions: Freezer (-20 or -80 degrees)
  - o Duration: Until testing
  - o Location: Leeds and Southmeads
  - o Long term storage: None

Responsibilities of the trial site in regard to samples: The trial site to ensure that samples are appropriately labelled in accordance with the trial procedures to comply with the 1998 Data Protection Act. Biological samples collected from participants as part of this trial will be transported, stored, accessed and processed in accordance with national legislation relating to the use and storage of human tissue for research purposes and such activities shall at least meet the requirements as set out in the 2004 Human Tissue Act and the 2006 Human Tissue (Scotland) Act.

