# 10 STATISTICS AND DATA ANALYSIS

## 10.1 Sample size calculation

This study is a pilot study intending to recruit 90 patients. We require 60 patients with blood samples collected for pharmacokinetic analysis. In approximately 30% of patients it is not possible to obtain blood samples for intra-operative technical reasons.

The full study sample size will be based on the following data:

- Alternative hypothesis: Pharmacodynamic target (4xMIC90 free serum concentrations) based continuous antibiotic dosing of antibiotic prophylaxis reduces the rate of surgical site infection after colorectal surgery by 50% when compared against standard antibiotic prophylaxis dosing regimes.

Justification: Ceftriaxone reduces surgical site infection in colorectal surgery by 39% compared to other cephalosporin regimes (odds ratio 0.61). It is believed this benefit is achieved by obtaining optimal PD targets. The PD target approach to antibiotic prophylaxis investigated in this study is attempting to obtain an equivalent benefit seen from ceftriaxone, without using ceftriaxone. We expect this 39% benefit to be restricted to patients who have operations over 2 hours. As 73% of patients have operations over 2 hours we expect the reduction in SSIs to be 53% (39/73).

Treatment Effect or Alternative Hypothesis: is this the smallest size of effect that would be of clinical interest- how is this justified in the form of appropriate references, pilot data or clinical arguments.

- Null Hypothesis: Pharmacodynamic target (4xMIC90 free serum concentrations) based continuous antibiotic dosing of antibiotic prophylaxis does not reduce the rate of surgical site infection after colorectal surgery when compared against standard antibiotic prophylaxis dosing regimes i.e. there is an absolute difference in response rates between arms of zero.
- Significance level: 0.05.
- Power: 90%
- Adjustments to sample size based on interim analysis(es)
- SSI rate in standard treatment group (operations > 2 hours)
  - 16.5% (estimated from elective patients only)
- SSI rate in investigation group: 50% of standard group=8.25%

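### For the standard-dosing arm, Table 5's fixed 1, 2, 3 and 4 h blood levels conflict with the sampling schedule in section 7.11; followed as written, they would under-read CMAX by about a third and often put the 4 h point after surgery.

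*Combined protocol and SAP*

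**What the plan says.** Section 3.6, Table 5, second row. The objective is "To determine exposure response relationships within patients treated with standard antibiotic dosing". The measures are free serum drug levels, MICs of colonising Enterobacteriaceae, fT>MIC and CMAX/MIC. The evaluation times are "1,2,3 and 4 hours post initiation of antibiotic prophylaxis".

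Section 7.11 describes the blood samples for drug concentrations, without limiting them to one arm: "4 samples taken intra-operatively". Their timing is as follows.

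- Early: "One sample will be collected at approximately 10 minutes after antibiotic infusion".
- Middle: "The other two samples will be taken after the surgery is approximately" one third and two thirds complete. One of these two may be moved to just before an intra-operative re-dose.
- Late: "One sample will be collected prior to closing the surgical wound".

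No other section settles which schedule applies. Section 7.7 lists antibiotic blood concentrations at Visit 2 without times, and the schedule of procedures in Appendix 4 has no blood-sampling row. Section 11.1 does plan a CRF that records prophylaxis and blood-collection timings.

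Two passages bear on operation length. The risk analysis in section 2.1 gives "53% <3 hours, 95% < 6 hours", and section 10.1 says "As 73% of patients have operations over 2 hours".

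**The concern.** One schedule is tied to the clock and starts at the pre-operative dose. The other is tied to the progress of the operation. They would place samples at different times in most patients, and the protocol describes no modelling step that turns one into the other.

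The Table 5 times also fit poorly with what Table 5 sets out to measure. CMAX after a bolus occurs early, and a first level at 1 h does not observe it. Late fixed times may come after the operation is over, so whether a late intra-operative level exists would depend on operation length. Section 1 cites gentamicin evidence that the level at the end of surgery was associated with efficacy; 7.11 captures that level, whereas hourly times do so only by chance. The comparator is also repeated at 4 h, so the 4 h sample coincides with the re-dose, and Table 5 does not say whether it is drawn before or after.

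At stake is the usefulness of the exposure-response description in the standard arm: a CMAX/MIC that is systematically low, and late levels that are missing in a way related to duration. Section 10.8 plans no strategy for missing data.

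**Working it through.** The plan states no figure that depends on the sampling times, so there is nothing of its own to reproduce. The check takes the two consequences in turn.

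**1. How much of the early level is left at 1 h (bolus arm)**

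Inputs: half-life 1.5 h (section 2.1, risk analysis); free cefuroxime of 21.5, 12.15, 7.8 and 4 mg/L at 1, 2, 3 and 4 h (Table 2).

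Log-linear fit to Table 2, with natural logs 3.068, 2.497, 2.054 and 1.386:

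- slope = [(-1.5)(3.068) + (-0.5)(2.497) + (0.5)(2.054) + (1.5)(1.386)] / 5 = -0.549 per hour
- half-life = 0.693 / 0.549 = 1.26 h

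Assuming one-compartment decay, the ratio of the 1 h to the 10-minute level is exp(-0.693 × (50/60) / half-life):

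- half-life 1.5 h: exp(-0.385) = 0.68
- half-life 1.26 h: exp(-0.458) = 0.63

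A highest observed level taken at 1 h is therefore 32-37% below the level 7.11 would record at 10 minutes.

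**2. How often the late fixed times fall after surgery**

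Inputs: F(2) = 1 - 0.73 = 0.27 (section 10.1); F(3) = 0.53 and F(6) = 0.95 (section 2.1), where F(t) is the share of operations finished by t hours.

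Assumptions:

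- The three shares describe the same population.
- F(4) is interpolated, since it is not given. Linear: 0.53 + (0.95 - 0.53)/3 = 0.67. Exponential: 1 - 0.47 × (0.05/0.47)^(1/3) = 0.78.
- The first dose precedes surgery by 0-1 h. Section 8.6 gives within the hour for the intervention loading dose, but says only pre-operative for the comparator.

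Among operations lasting over 2 h, the share finished by t is (F(t) - 0.27)/0.73.

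| Table 5 point | Lead | Time into surgery | Share of operations over 2 h already finished |
|---|---|---|---|
| 3 h | 1 h | 2 h | (0.27 - 0.27)/0.73 = 0% |
| 3 h | 0 h | 3 h | (0.53 - 0.27)/0.73 = 36% |
| 4 h | 1 h | 3 h | (0.53 - 0.27)/0.73 = 36% |
| 4 h | 0 h | 4 h | (0.67 - 0.27)/0.73 = 55% (linear) to 69% (exponential) |

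So the range is 36-69% for the 4 h point and 0-36% for the 3 h point. If the 53% and 95% already refer only to operations over 2 h, the shares apply directly: 53-78% for the 4 h point and 0-53% for the 3 h point.

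**3. Do the schedules coincide anyway?**

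Under 7.11 the middle samples fall at 0.67 and 1.33 h into a 2 h operation, and at 2 and 4 h into a 6 h operation. They do not line up with a fixed hourly grid in general, and Table 5 has no counterpart to the 10-minute sample.

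**The case against.** The strongest reply is that 7.11 is the operational sampling section, while the Table 5 column lists times at which an outcome is evaluated. If staff follow 7.11, neither the loss of CMAX nor the missing late levels arises. That is fair, and it makes the bias conditional. It does not remove the conflict: the protocol neither says that 7.11 governs nor describes how levels at 1-4 h would be obtained from samples taken at other times. A population model could back-extrapolate the peak, but none is specified.

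Table 5 taken alone also does not say its samples are intra-operative. That restriction comes from 7.11, so draws after surgery are not ruled out. Nor are hourly times useless for fT>MIC: in Table 2 the standard-dose free level crosses 16 mg/L between 1 and 2 h and 8 mg/L just before 3 h. The mismatch is clearest for CMAX and for the end-of-surgery level.

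A reader might infer more than the documents support.

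- *That operations ending before 3 h would yield at most two intra-operative samples.* The clock starts before surgery. With a 45-minute lead, the 3 h sample falls 2.25 h into surgery, inside a 2.5 h operation. Only the 4 h point is firm.
- *That the pilot's 60 patients with blood samples are compromised.* Section 10.1 gives that number for pharmacokinetic analysis generally. The Table 5 row covers one arm, and the bolus-decay calculation does not carry over to the continuous infusion.
- *That actual sample times would be lost.* Section 11.1 already puts them on the CRF.
- *That the missing levels would be tied to SSI risk.* The documents do not quantify a link between operation length and SSI. They support only a link between missingness and duration.

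**Conclusion.** The conflict is in the current text and should be reconciled. Followed as written, the Table 5 times would make observed CMAX in the standard arm about a third too low (1 h level 63-68% of the 10-minute level). They would place the 4 h point after surgery in roughly 36-69% of operations over 2 h, and the 3 h point in 0-36%.

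The first figure rests on one-compartment decay after a bolus. The others rest on the assumed lead, the interpolated 4 h share, the duration figures sharing one population, and actual durations exceeding 2 h, although eligibility is set on expected duration. The 10-minute and fractional times in 7.11 are themselves approximate.

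The reach is modest: an exploratory exposure-response endpoint in one arm. The primary SSI comparison is not affected.

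**What to change.** - In Table 5, replace the fixed times with the 7.11 schedule: about 10 minutes after infusion, about one third and two thirds of surgery, and before closure, with the option to move one middle sample to before a re-dose.
- Add a matching blood-sampling row to Appendix 4.
- State that CMAX/MIC and fT>MIC are derived from actual dose and sample times. Section 11.1 already provides for these on the CRF, so this needs only confirmation that both are entered as clock times.

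While editing, say what the 10 minutes in 7.11 is counted from for patients on the continuous infusion, where the phrase is unclear.

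The cost is a small text amendment. The number of samples and the burden on patients do not change.

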#### 4 TRIAL DESIGN

Colo-Pro Pilot: A pilot randomised controlled single blind trial to compare standard single dose of antibiotic prophylaxis to antibiotic prophylaxis administered as a continuous infusion for the prevention of surgical site infections in adults undergoing colorectal surgery.

#### 5 STUDY SETTING

- Leeds Teaching Hospitals NHS Trust
- Interventions will be carried out by the following staff
  - Recruitment and allocation: Research nurse or research doctor
  - Intervention: Anaesthetist and surgeon, supported by a research nurse or research doctor.
  - Sample collection: Rectal swab and blood samples: Research nurse or research doctor
  - Outcome data collection: Research nurse or research doctor.

## 6 ELIGIBILITY CRITERIA

This study is pragmatic as it is intended that the intervention would be applied to all patients undergoing colorectal surgery, emergency and elective, with varied indications for surgery, and varied risks of surgical site infections.

### 6.1 Inclusion criteria

- Undergoing colorectal surgery (incision, excision or anastomosis of the large bowel, including anastomosis of small to large bowel)
- Age >18.
- Expected duration of surgery > 2hours
- Creatinine clearance > 40 ml/min
- Cefuroxime/metronidazole are appropriate antibiotic prophylaxis regimens.
- Patient capable of giving informed consent
- Patients undergoing colorectal surgery plus additional surgery e.g. plastic surgery, urological surgery, gynaecological surgery.
- If it is not possible to obtain intra-operative blood samples e.g. difficult vascular access, or pre-operative swabs e.g. anatomy makes it difficult to obtain, patients will be included and this information treated as missing data. Patients on antibiotic treatment for an existing infection (except SSIs) can be included in the study

### 6.2 Exclusion criteria

- Unable to consent
- Pregnancy
- Expected duration of surgery <2hours
- Creatinine clearance <40ml/min
- Individual level microbiological advice for non cefuroxime based prophylaxis
- Cephalosporin allergy
- Penicillin allergy (hypersensitivity reaction only)
- Coumarin (warfarin and acenocoumarol) treatment
- Active blood borne virus infection e.g. HIV, hepatitis.
- Seizure history
- Concurrent use of probenecid
- Current participation in a research project aimed at reducing SSIs
- Antibiotics for treatment of a systemic Gram negative infection within 2 hours of initiation of surgery (Vancomycin, Teicoplanin, Daptomycin, Linezolid, Flucloxacillin. Nitrofurantoin and Clarithromycin would be permissible antibiotics without systemic Gram negative antibiotics).
- A current diagnosis of an SSI at the time of study entry.
- STARR procedures
- Weight <30kg or >110kg

Duration of the risk mitigation measures: 24 hours

MPs are not teratogenic

## 7 TRIAL PROCEDURES

Schedule of procedures: Appendix 4.

### 7.1 Recruitment

Participants who are screened for trial entry and are not randomised will have data collected for Consolidated Standards of Reporting Trials (CONSORT) reasons to allow reporting of the generalisability of the results. Anonymised information on participants who are not randomised for will include: Age, Gender, whether the patient is registered or not registered, the reason not eligible for trial participation, or if they are eligible but declined, the procedure they were due to undergo, if the procedure was elective or an emergency procedure and the ASA score.

#### 7.1.1 Patient identification

Participant eligibility screening process

Patients will be identified for trial entry by a number of methods including:

- Notification by a member of the patient's clinical team, to the research team, a patient is due to undergo colorectal surgery. This may happen after the patient has been seen:
  - o In the outpatient setting
  - o As a hospital in patient
- Identification by a member of the research team a patient is due to undergo colorectal surgery by screening of hospital surgical theatre lists.

Both the clinical team and the research staff will hold a contract, permanent or honorary, with their host hospital. All recruiting staff will therefore be part of the patient's normal clinical staff.

The research team will include medical and nursing staff. Eligibility will be confirmed by a medical practitioner.

#### 7.1.2 Screening

- No diagnostic testing is required to confirm eligibility
- Penicillin/cephalosporin allergy will be assessed

### 7.2 Consent

The Principal Investigator (PI) retains overall responsibility for the informed consent of participants at their site and will ensure that any person delegated responsibility to participate in the informed consent process is duly authorised, trained and competent to participate according to the ethically approved protocol, principles of Good Clinical Practice (GCP) and Declaration of Helsinki.

Delegation of consent:

Informed consent will be obtained prior to the participant undergoing procedures specifically for the purposes of the trial

The right of a participant to refuse participation without giving reasons will be respected.

The participant will remain free to withdraw at any time from the trial without giving reasons and without prejudicing his/her further treatment and will be provided with a contact point where he/she may obtain further information about the trial.

The PI takes responsibility for ensuring that all vulnerable subjects are protected and participate voluntarily in an environment free from coercion or undue influence

Translation:

To comply with the Welsh Language Act 1993, the Participant Information Sheets and Consent forms will be translated into Welsh or provided bilingually where this is requested by a participant at a research site.

The protocol will fully describe the process which typically involves:

Consenting protocol involved:

- Discussion between the potential participant or his/her legally acceptable representative and an individual knowledgeable about the research about the nature and objectives of the trial and possible risks associated with their participation
- The presentation of written material (Patient information leaflet and consent form, approved by the REC and in compliance with GCP, local regulatory requirements and legal requirements)
- The opportunity for potential participants to ask questions
- Assessment of capacity. Participants must be capable of giving consent for themselves. A capable person will:
  - understand the purpose and nature of the research
  - understand what the research involves, its benefits (or lack of benefits), risks and burdens
  - understand the alternatives to taking part
  - be able to retain the information long enough to make an effective decision.
  - be able to make a free choice
  - be capable of making this particular decision at the time it needs to be made (though their capacity may fluctuate, and they may be capable of making some decisions but not others depending on their complexity)
  - where participants are capable of consenting for themselves but are particularly susceptible to coercion, it is important to explain how their interests will be protected

Where a participant is able to consent but later becomes incapacitated the participant would be withdrawn from the study. Identifiable data or tissue already collected with consent would be retained and used in the study. No further data or tissue would be collected or any other research procedures carried out on or in relation to the participant.

### **7.2.1 Additional consent provisions for collection and use of participant data and biological specimens in ancillary studies, if applicable**

- Data and biological specimens including bacteria from rectal swabs and blood samples for antibiotic drug concentrations will be acquired and stored during the trial.
- Participation in the ancillary research is required for participation in trial. A single consent will be obtained for the use of rectal swabs samples and blood samples for antibiotic drug concentrations in planned and future research related to the clinical condition under study only.

### 7.3 The randomisation scheme

Simple randomisation with a 1:1 allocation ratio will be used to allocate patients.

#### 7.3.1 Method of implementing the allocation sequence

The allocation sequence will involve:

- generation of an unpredictable allocation sequence
- concealment of that sequence until assignment irreversibly occurs.

The system to use be used a web based randomisation/treatment allocation system

Research nurses and research doctors recruiting patients will access this at the research

- The allocation system will provide sealed envelopes to be accessed upon a decision to allocate a participant to a treatment arm.
- Documentation of the randomisation arm will be added to the patient notes in a sealed document holder for access in case of medical need only.
- Documentation of the randomisation will be provided to a research database accessible to researchers.

